To address Aims 2,3,4: Among 210 SO and 315 RA families (i.e., total N=525 families) with 5-12 year-old children, we will examine effects of ADAPT modalities and sequences/timing on multiple behaviors and outcomes (i.e., (i) coercive family interactions, positive parenting, couple adjustment, and co-

parenting, (ii) parents PTSD symptoms, depression symptoms, substance use, (iii) child behavior and emotional problems, and positive adjustment, by conducting a 2-stage SMART, and (iv) document participation, satisfaction, and fidelity. To assess behaviors and outcomes, we will administer and collect a series of assessments (Table 1 appendix) at 4 timepoints.

For Aims 2, 3, and 4, we will use a 2-stage SMART design to examine the optimal sequence, dosage, and delivery formats of ADAPT for active duty military families living in a range of operational tempo contexts. We will recruit a total of 525 families living on three installations: Fort Bragg (North Carolina), Fort Campbell (Kentucky) and Forts Belvoir/Myer, with 210 families recruited from Fort Bragg and Fort Campbell and 105 from Forts Belvoir/Myer.

5.2 Study Procedures:

Subjects for this study include: (I) 525 active duty clinical trial participants recruited from 4 bases who will be randomized to first stage (brief interventions) and second stage (more intensive booster ADAPT programs for families who do not benefit from the first stage interventions); (II) Twelve current study families (N = 24) who will participate in focus groups; (III) 525 children participants between the ages of 5-12 of clinical trial participants who will be asked to participate in assessments only; (IV) Up to 1890 teachers who will be asked to complete the Behavior Assessment System for Children, Second Edition (BASC-3) each yr that the child is in the study (usually 3 grades)

Focus group Participants

We will hold two focus groups with study parents to inform program modifications. Each focus group will consist of 12 participants, one group Special Operations (SO) participants and one group Regular Army (RA) participants, both on Fort Bragg, NC.

Clinical Trial Participants

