Active duty families will be living in a range of operational tempo (OPTEMPO) contexts (i.e., Regular Army/RA and Special Operations/SO) on one of four military installations. All participants will be in units with deployments occurring during the study period. 525 families will be recruited from target bases as follows: (a) Fort Bragg, NC – 210 families recruited, including 105 SO and 105 RA. (b) Forts Belvoir/Myer, VA – 105 Active Duty families recruited. (c) Fort Campbell, KY– 210 families recruited, including 105 SO and 105 RA.

Clinical Trial Participants will be asked to do the following:

- (1) Complete assessments at four time points. Assessments are listed and described below and included on the final page of the protocol.
 - a. T1 (baseline (BL) and prior to the start of the intervention); both on-line and in-home data is collected from families; child self-report measures will be gathered and are standardized with children over 5.
 - b. Responder Checkpoint – Parent Locus of Control 22-item questionnaire completed by parents 4 weeks after they start the intervention

- c. T2 (6 months following baseline); only online parent data will be gathered, (no in-home assessment)
 - d. T3 (12 months following BL, i.e. following the end of the reintegration session(s) and program completion); both on-line and in-home data is collected from families, child self-report measures will be gathered from children over age 5.
 - e. T4 (24 months after BL); both on-line and in-home data is collected from families, child self-report measures will be gathered from children over age 5.
2. Participate in videotaped (with audio) in-home parent-child interaction tasks lasting a total of 30 minutes at three time points (BL/T1, T3, and T4). These interaction tasks are administered and videotaped by trained assessment technicians in the participants' homes. If preferred, participants may complete assessments outside the home at project offices. Video and audio of study participants will be accessed only by the investigators and trained members of the coding team.
3. Fill out online questionnaires at the time of in-home assessments (BL/T1, T3, and T4).

Note: childcare provided by study staff is offered during in-home assessments for siblings. If study staff are not available to provide childcare, a \$30 gift card stipend will be offered to the family so that they can arrange their own childcare.

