- b. If participating families have more than one child between the ages of 5 and 12, staff will randomly select the child to participate in the study. Children are included in the assessment phase only to examine the effectiveness of ADAPT in reducing risk for substance use, child maladjustment, and related behavior problems.

Teachers will be asked to do the following:

Up to 1890 teachers will be asked to complete the BASC-3, a 100-139 item instrument designed to evaluate various aspects of behavior and personality in children, youth, adults ages 2-25. The BASC-3 takes between 10-20 minutes to fill out. Teachers will be asked to fill out the questionnaire at T1, T3, and T4. In addition, teachers will be asked to complete the TPRISK - a measure on deviant peer association.

ADAPT is a resilience-building program designed to strengthen families through the transitions associated with deployment, targeting multiple outcomes in service members, spouses, children, and families. This study will yield knowledge about the optimal components, sequence, and dosage for improving family adjustment in diverse OPTEMPO contexts, yielding an efficient, scalable and sustainable universal prevention intervention to strengthen the family at home, and the soldier's functioning at home and in the field.

Potential Risks

Potential discomfort and risks participants may experience as a result of their involvement in this study include the following:

1. Discomfort with assessment procedures (e.g., videotaping)
2. Discomfort in disclosing sensitive information
3. Violation of confidentiality as a result of compliance with mandatory reporting requirements
4. A possible violation of confidentiality due to mishaps with identified data
5. Discomfort resulting from misunderstanding the planned use of data

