17.0 Data Management

17.1 Data Analysis Plan:

Analyses will be conducted in several steps, starting with preliminary and preparatory analyses including data reduction and evaluation of psychometric properties, followed by evaluation of missing data of criterion measures. For the primary efficacy evaluation aims of main effect components and the four adaptive intervention strategies we will employ standard normal theory Analysis of Covariance factorial and fractional factorial analyses to address study aims using pre-post assessment scores for parent and child adjustment constructs. To address the non-independence of subjects in the embedded adaptive intervention designs we will estimate Linear mixed models and weighted least squares regressions for estimation of the embedded adaptive intervention contrasts. Descriptive statistics (mean, range, SD) will be used in reporting participation, satisfaction (for fathers and mothers), and implementation fidelity (for each provider and the group of ADAPT providers).

17.2 Power Analysis:

First, we chose a power convention of .80 with a two-sided alpha level of .05 to reduce the probability of obtaining a false positive improvement or intervention effect rejecting the null when it is true (Type-I error at 5% chance). Second, we powered the study to detect small to medium effect sizes for the first and second stage randomizations. The first stage randomization is allocated with a 1:1 ratio to group conditions as depicted in Figure 6. Based on the ROC analyses we estimate a potential 50% non-response rate for both the online and weekend condensed groups. After the Week 4 assessment of response criteria, non-responders will also be randomized to second stage interventions with a 1:1 allocation.

More specifically, power needed to be estimated by addressing the restricted randomization scheme and appropriate weighting of the overrepresentation of responders and underrepresentation of nonresponders. We employed procedures outlined by Oetting and colleagues for estimating power in SMART trial designs. As recommended, we specified an alpha level of .10 and power of .80. The first main research question (2a) addresses main effects of initial stage randomization,

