The assessment package includes self-report measures (Table 1) to be completed by each participating parent or caregiver. The assessment package takes each adult approximately 35 minutes to complete, and upon completion participants are each compensated \$25 (per assessment package completed; up to two per family). Parents also are asked to schedule a 15-minute study orientation call, and in-home assessment appointment with project staff. Families who do not complete the online assessment will be asked to complete the assessment during the assessment in-home visit.

(6). A copy of the parental consent form will be offered to and left with families at the first (BL) in-home visit and all subsequent visits (T3 and T4).

(7). Child assent will be completed at the first (BL) in-home assessment. The assent form is attached.

a. In-home assessments will be conducted by pairs of well-trained research assistants located on or near each base who will be employees of the University of Minnesota with extensive experience with military families (as veterans, spouses or relatives, and/or service providers) and with some research experience. They will be provided extensive training in data privacy, HIPAA, human subjects' protection, the consent process, and assessments.

Note: childcare provided by study staff is offered during in-home assessments for siblings. If study staff are not available to provide childcare, a \$30 gift card stipend will be offered to the family so that they can arrange their own childcare.

b. Families who prefer assessment outside the home may go to the local project office. Following the BL assessment, participants are electronically (via computer program) given random assignment to clinical trial conditions, which have been explained during the consent process.

c. Teachers will be contacted via secure, encrypted email, with an explanation of the study, and a copy of the parent's release of information (see attached) . They will be directed to the study website to complete questionnaires. Teachers not

responding will receive materials by mail, with follow-up calls (this has been a very effective strategy in our prior studies).

22.2 Waiver or Alteration of Consent Process (when consent will not be obtained, required information will not be disclosed, or the research involves deception):

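### The protocol promises findings for diverse OPTEMPO contexts and recruits to SO/RA cells, but no SO/RA analysis is planned or powered, so only pooled conclusions follow

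*Combined protocol and SAP*

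**What the plan says.** **Purpose.** Section 5.1 says the design is used "to examine the optimal sequence, dosage, and delivery formats of ADAPT for active duty military families living in a range of operational tempo contexts". Section 5.2 says the study will yield knowledge about the "optimal components, sequence, and dosage for improving family adjustment in diverse OPTEMPO contexts".

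**Recruitment.** Section 5.1 gives the totals: "Among 210 SO and 315 RA families (i.e., total N=525 families"). Section 5.2 breaks them down: "Fort Bragg, NC – 210 families recruited, including 105 SO and 105 RA"; the same split at Fort Campbell; and, at Forts Belvoir/Myer, "105 Active Duty families recruited", with no SO/RA split. That makes five cells of 105.

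**Assignment.** Section 22.1 says that after baseline "participants are electronically (via computer program) given random assignment to clinical trial conditions". Section 17.2 adds: "The first stage randomization is allocated with a 1:1 ratio to group conditions as depicted in Figure 6". That figure is not available to us. Second-stage allocation of non-responders is also 1:1. No stratification factor is named at either stage.

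**Analysis.** Section 17.1 plans factorial and fractional factorial ANCOVA on pre-post scores, with mixed models and weighted least squares for the embedded strategies. It names no installation or SO/RA term. The section 17.2 table covers three pooled questions: Q2a (first-stage main effect), Q2b (second-stage main effect in non-responders) and Q2c (best strategy). The one covariate named besides the pre-scores is relationship status, in section 9.1.

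**The concern.** The trial recruits SO and RA families in planned numbers and says it will inform practice across OPTEMPO contexts. Yet an analyst who follows section 17 to the letter will produce one pooled answer per question. Two outcomes are then likely. Either the pooled result is reported as if it had been shown in both contexts, or SO/RA comparisons are run after the fact with no stated sensitivity. In the second case a non-significant interaction could be taken to mean that the program works equally well for SO and RA families, when the data could not show otherwise unless the difference were large.

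**Working it through.** **1. Inputs.** 105 SO and 105 RA at each of Bragg and Campbell, and 105 at Belvoir/Myer (section 5.2). Attrition 10% to 20%, power .80, and alpha stated both as two-sided .05 and as .10 (section 17.2). Both alphas are carried through; z sums are 1.645 + .842 = 2.487 and 1.960 + .842 = 2.802. Effects are in SD units, with 1:1 allocation and families taken as independent.

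**2. The plan's own figure.** For a two-arm comparison, MDE = z sum × sqrt(4/N). For Q2a with N = 473:
- two-sided .10: 2.487 × sqrt(4/473) = .229
- two-sided .05: 2.802 × sqrt(4/473) = .258

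The table states .324, so it does not reproduce from its listed N. It does match two-sided .10 with half that N: 2.487 × sqrt(4/236.5) = .323. The documents do not explain this. The interaction below is therefore compared with .229 and .258 from the same formula, and the table value is not rescaled.

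**3. First-stage arm × SO/RA at Bragg and Campbell.** Each group has 210 × .90 = 189 families. The arm effect within a group has variance 4/189, so the difference between two such effects has variance 8/189 and standard error sqrt(8/189) = .206.

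| | Interaction MDE | Pooled Q2a MDE |
|---|---|---|
| two-sided .10 | 2.487 × .206 = .51 | .23 |
| two-sided .05 | 2.802 × .206 = .58 | .26 |

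The ratio is sqrt((8/189)/(4/473)) = 2.2. With 20% attrition (168 v 168) the interaction MDE is .54 or .61.

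**4. What a null would mean.** An estimated interaction of exactly zero would carry a 95% interval of ±1.96 × .206 = ±.40 SD. That is wider than the pooled MDE, so it would not show equal effects.

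**5. Counting Belvoir/Myer as RA.** The 315 RA total in section 5.1 requires this (105 + 105 + 105). The comparison is then 189 v 283.5, and sqrt(4/189 + 4/283.5) = .188 gives .47 or .53. The message is unchanged. Section 12.2 describes several service branches there, so RA is not a clean label for that site.

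**6. Second stage.** At the plan's 50% non-response, again counting Belvoir/Myer as RA, sqrt(4/94.5 + 4/141.75) = .266 gives .66 or .74. A second-stage moderator test would tell the reader little.

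**7. Precision from adjusting for the cells.** The MDE scales by sqrt(1 − R²), where R² is the share of outcome variance the cells explain beyond the pre-score. The documents give no R², so it is assumed:
- 1%: MDE 0.5% smaller
- 3%: 1.5% smaller
- 5%: 2.5% smaller
- 15%: 7.8% smaller

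**8. Cost of not stratifying, once cells are in the model.** A simulation of five equal cells (5,000 draws) gives an efficiency loss of about 0.9% at N = 473 and 1.7% at N = 236.

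**The case against.** The best defense is that the OPTEMPO wording in section 5.1 describes the population and is not a hypothesis. All three research questions are pooled, and recruiting SO families can simply serve representativeness. That is a fair reading of section 5.1. It fits less well with the section 5.2 statement, which offers knowledge for diverse OPTEMPO contexts as a product of the study. A second defense is that section 17.1 is not a full covariate list, since relationship status appears only in section 9.1. That shows the cells are not ruled out; it does not show that they are planned.

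A reader might infer more than the documents support:

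- **That assignment is unrestricted.** The text is silent on stratification and the cited figure is not available. The phrase about a restricted scheme in section 17.2 appears to concern the re-randomization of non-responders and its weighting, so it settles nothing about site or OPTEMPO.
- **That the cells are known to be prognostic.** No section says so. Unadjusted comparisons remain valid, and any precision gain rests on an assumed R².
- **That no OPTEMPO-specific answer could ever emerge.** SO/RA status is known at Bragg and Campbell, so estimates can be made. They would be unplanned and without stated power.
- **That Q2b ignores first-stage program.** The table gives a contrast, not a model. A factorial ANCOVA may well include first-stage arm; this needs confirming.
- **That blocking should be introduced now.** Working step 8 shows little to gain, and changing the assignment scheme partway through would leave two schemes to account for.

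It is also true that the proposed interaction is insensitive and does not answer Q2c by OPTEMPO. That is a reason to state its limits in advance.

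**Conclusion.** The concern holds as a gap between the promised conclusion and the planned analysis. No stratification factor is specified, section 17 names no installation or SO/RA term, and no OPTEMPO moderation analysis is planned or powered. The pooled comparisons are not invalid, and the precision at stake is minor. What matters is interpretation: even a planned first-stage moderator test would detect only a difference of about half an SD or more, 2.2 times the pooled MDE. These sizes assume 1:1 allocation within SO and RA, 10% attrition in each, independent families and a common SD. Clustering of families in workshops would make the test less sensitive still. It is worth acting on because the changes are nearly free.

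**What to change.** 1. In section 17.1, enter the five recruitment cells as fixed effects in the Q2a, Q2b and Q2c models, and confirm that first-stage arm is a factor in the Q2b factorial ANCOVA. Cost: four degrees of freedom for the cells and one for the arm, using data already collected.
2. Pre-specify first-stage arm × SO/RA at Bragg and Campbell as the single secondary moderator test. Report the estimate with its interval. State the MDE in advance (.51 SD at two-sided .10 or .58 SD at two-sided .05), name which of the two alphas in section 17.2 applies, and say that a null is not evidence of equal effects.
3. Reword the section 5.2 conclusion as pooled across OPTEMPO contexts unless that test supports more. Say plainly that the test does not identify the best strategy (Q2c) by OPTEMPO.
4. State whether assignment was stratified and, if so, by what. No change to the assignment scheme is asked for.

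These are text edits to the analysis plan. Sample size, interventions and data collection are unaffected.

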6.0 Data Banking

NA

7.0 Sharing of Results with Participants

NA

8.0 Study Duration

8.1 Describe:

- Study participants can expect to be involved in the study for 2 years.
- 21 months (complete recruitment May 2018).
- 4 years (complete study September 30, 2020).

9.0 Study Population

9.1 Inclusion Criteria:

Recruitment is limited to families meeting the following inclusion criteria: (a) one parent has returned from deployment (b) at least one child age 5 to 12 in their custody and living with parent(s) in the home. (c) We will include both single- and two-parent families, as well as families where care is shared between non-partnered adults (e.g. grandparent and mother), and will control for relationship status in the analyses. (d) Participants must agree to randomization, and (e) indicate willingness to interact with study materials and complete assessment

batteries. Women and minorities are included in the study. Inclusion criteria (a), (b), (c), (d), and (e) are necessary to meet the specific aims of the study and to meet the requirements of PMTO/ADAPT.

9.2 Exclusion Criteria:

Exclusion criteria include: (a) families with children younger than 5 or older than 12 – see the above rationale for the age limitation of children; (b) parent has an active psychosis, (c) an open child protection case for abuse or neglect in the family, (d) a serious child mental health diagnosis, i.e., autism, child psychosis (e) youth do not meet age criteria, (f) youth have a documented pervasive developmental disability or mental retardation, (g) less than a 5th grade comprehension level in English. Children and families will not benefit from a prevention intervention if either the parent or the child has a serious mental illness, if the family has an active child protection case, or if the parents are not able to comprehend the materials.

Screening:

Potential participants will be asked to take an online eligibility survey that will screen for inclusion criteria.

10.0 Vulnerable Populations

10.1 Vulnerable Populations:

- Children
- Pregnant women/Fetuses/Neonates
- Prisoners
- Adults lacking capacity to consent and/or adults with diminished capacity to consent, including, but not limited to, those with acute medical conditions, psychiatric disorders, neurologic disorders, developmental disorders, and behavioral disorders
- Non-English speakers
- Those unable to read (illiterate)
- Employees of the researcher
- Students of the researcher
- None of the above

10.2 Adults lacking capacity to consent and/or adults with diminished capacity to consent:

NA

10.3 Additional Safeguards:

Potential Risks

Potential discomfort and risks participants may experience as a result of their involvement in this study include the following:

1. Discomfort with assessment procedures (e.g., videotaping)
2. Discomfort in disclosing sensitive information

3. Violation of confidentiality as a result of compliance with mandatory reporting requirements
 4. A possible violation of confidentiality due to mishaps with identified data
 5. Discomfort resulting from misunderstanding the planned use of data
- Participation in this research involves minimal risk, defined in the Federal guidelines, as “the probability and magnitude of harm anticipated in the research are not greater in and of themselves than those ordinarily encountered in daily life or during the performance of routine physical or psychological examinations or tests.” (Federal Register, 1991, 45CFR 46.102(i). Procedures are in place to minimize risk of violation of confidentiality, as indicated: If the study child or participating caregiver discloses information regarding child abuse or threat to self or others, professionals are mandated to report the information to appropriate authorities. This information will be clearly stated verbally and on the consent forms. It is not likely that participants will experience physical, social or legal risks due to enrollment in the study because state mandated procedures exist to protect them. There are no financial risks to participants. Procedures are in place for providing suitable informed consent, clearly describing the assessment activities, emphasizing the voluntary nature of the study, and communicating the purpose and use of the data collected. These procedures are intended to minimize participant’s misunderstanding of or dissatisfaction with the research.

Practices to minimize the risk with children.

- a. The informed consent process for child participation will be conducted during the in-home assessment process. The study, procedures, and tasks of the study will be explained to both the parent and the child. Both child assent and parental consent forms will be presented to the family and explained.
- b. The research staff conducting the informed consent process will ask each child to explain the study process in their own words to assure that they understand what is being asked of them and what they will be asked to do (e.g. answer questions, play a game with their parents, be willing to be video-taped while playing the game).
- c. Research staff will ask both the parent and child, separately and directly, if they have any questions or concerns about the study. It will be stated very directly to the child that no one will be angry or upset with them if they decide not to participate in the study and that they can change their mind or ask more questions at any time during the study.
- d. Once the research staff has been able to ascertain that both the child and the parent understand the procedures of the study and what the child will be asked to do, written signatures will be requested from the parent and child on both the Child Assent form and the Parental Consent form.

